Appendix A. Schedule of Assessments (Part 1 and Part 2)

Study Procedures ^{a,r}	Screening		Week																					
	-35 days	-7 days	1	2	3	4	5	5			6	7	8	9	10	11	12	13	14	15	16	17	18	19
Hour (D = day)								D1	24 D2	48 D3	96 D5													
PK Collection window ^k								± 4 hrs																
General Assessments ^r																								
Consent & eligibility review	X																							
Vital Signs ^b	X ^e		X		X		X					X		X		X		X		X X			X	
PE, height, weight & ECOG ^b	X ^e		X				X						X				X					X		
ECG ^c		X																						
Review of AEs, SAEs, commeds ^d	X		X		X		X					X		X		X		X		X X			X	
Local Laboratory Tests ^{t,r}																								
Hematology		X ^e			X		X					X		X		X		X		X X			X	
Chemistry ^g		X ^{eg}			X		X ^g					X		X ^g		X		X ^g		X		X ^g		X
PT and INR (Part 2)							X									X							X	
HgbA1c		X					X							X			X					X		
TSH		X					X						X			X			X			X		
CEA		X ^e											X ^f				X				X			
Urine/Serum Pregnancy (-3 days) ^f		X ^e																						
Central Laboratory Sample Collection ^{h,r}																								
Tumor Tissue ⁱ	X ⁱ																							
PK (Part 1) ^{j,f}			X				X	X X X			X	X						X						
PK (Part 2) ^{k,f}			X		X		X				X						X							
Biomarker		X	X										X											
Antibodies ^{lp}		X									X													
Investigational Product Administration ^r																								
Review dose adjustment criteria ^m				X		X					X		X		X		X		X X			X		
Investigational product admin. ^m			X	X	X						X		X		X		X		X X			X		
Radiological Assessments ^{n,r}																								
CT/MRI-Chest, Abdomen, & Pelvis	X ^e											X				X				X				
Investigator Assessment of Tumor Response											X				X			X			X			

Approved

Appendix A. Schedule of Assessments (continued)

(Part 1 and Part 2)

Study Procedures ^{a,r}	Week																											
	21	22	23	24	25	26	27	28	29	30	31	32	33	34	35	36	37	38	39	40	41	42	43	44	45	46	47	48
General Assessments^r																												
Vital Signs ^b	X		X		X		X		X		X		X		X		X		X		X		X		X		X	
PE, weight & ECOG ^b	X			X			X			X			X			X		X		X		X		X		X		
Review of AEs, SAEs, & conmeds ^d	X		X		X		X		X		X		X		X		X		X		X		X		X		X	
Local Laboratory Tests^{t,r}																												
Hematology	X		X		X		X		X		X		X		X		X		X		X		X		X		X	
Chemistry ^g	X ^g		X																									
PT and INR (Part 2)			X						X					X				X			X						X	
HgbA1c	X			X			X				X			X			X			X			X			X		
TSH	X			X			X			X			X			X			X			X			X			
CEA				X							X									X							X	
Central Laboratory Sample Collection^{h,r}																												
PK (Part 1) ^{if}			X																									X
PK (Part 2) ^{kt}			X																									X
Antibodies ^{ip}			X																									X
Investigational Product Administration^r																												
Review dose adjustment criteria ^m	X		X		X		X		X		X		X		X		X		X		X		X		X		X	
Investigational product administration ^m	X		X		X		X		X		X		X		X		X		X		X		X		X		X	
Radiological Assessments^{n,r}																												
CT/MRI - Chest, Abdomen, & Pelvis				X								X								X							X	
Investigator Assessment of Tumor Response				X							X									X							X	

Approved

Appendix A. Schedule of Assessments (continued)

(Part 1 and Part 2)

Study Procedures ^{a,r}	Week 49 until Radiographic Disease Progression Visits repeated every 12 weeks (unless otherwise indicated)												30-Day Safety Follow-up Visit (+3 day window)	60-Day Follow-up Visit (+14 day window)	LTFU (± 28 day window)	End of Study ^q
	1	2	3	4	5	6	7	8	9	10	11	12				
General Assessments^r																
Vital Signs ^b	X		X		X		X		X		X		X			
PE, weight & ECOG ^b	X				X			X					X			
Review of AEs, SAEs, & conmeds ^d	X		X		X		X		X		X		X			
Review inclusion criteria for part 3 (see Section 4.3 & Appendix B) ^o													X ^o			
Local Laboratory Tests^{t,r}																
Hematology	X		X		X		X		X		X		X			
Chemistry ^g	X ^g		X		X ^g		X		X ^g		X		X ^g			
PT and INR (Part 2)	X					X							X			
HgbA1c	X				X			X					X			
TSH	X			X				X					X			
CEA											X		X			
Central Laboratory Samples^{h,r}																
PK (Part 1) ^l												X ^l	X	X		
PK (Part 2) ^k												X ^k	X	X		
Biomarker													X	X		
Antibodies ^{ip}												X	X	X ^l	X ^p	
Investigational Product Administration^r																
Review dose adjustment criteria ^m	X		X		X		X		X		X					
Investigational product administration ^m	X		X		X		X		X		X					
Radiological Assessments^{n,r}																
CT or MRI of Chest, Abdomen, & Pelvis											X		X ^{np}		X ^{np}	
Investigator Assessment of Tumor Response											X		X ^{np}		X ^{np}	

Approved

Appendix B. Schedule of Assessments (Part 3)

Study Procedures ^{a,r}	Qualification	Week	1	2	3	4	5	6	7	8	9	10	11	12	13	14	15	16	17	18	19	20
General Assessments																						
Review inclusion criteria for part 3 (see Section 4.3)	X ^o																					
Unblind in IVRS Note: only eligible subjects may be randomized in part 3 (see Section 7.2)	X ^o																					
Vital Signs ^b			X		X		X		X		X		X		X		X		X		X	
PE, weight & ECOG ^b	X	X			X			X							X			X				
Review of AEs, SAEs, & conmeds ^d	X		X	X		X		X				X		X		X		X		X		
Local Laboratory Tests^{f,r}																						
Hematology	X	X		X		X		X		X		X		X		X		X		X		
Chemistry ^g	X	X ^g		X	X ^g		X		X ^g		X		X ^g		X		X ^g		X ^g		X	
PT and INR		X			X								X								X	
HgbA1c	X	X			X				X						X				X		X	
TSH	X	X			X			X						X			X			X		
CEA	X							X ^t					X				X					
Central Laboratory Tests^{h,r}																						
Biomarker			X						X													
Antibodies ^{ip}		X					X															
Investigational Product Administration^r																						
Review dose adjustment criteria ^m				X		X		X		X		X		X		X		X		X		
Investigational product administration ^m		X		X		X		X		X		X		X		X		X		X		
Radiological Assessments^{n,r}																						
CT/MRI - Chest, Abdomen, & Pelvis									X				X			X		X				
Investigator Assessment of Tumor Response									X				X			X		X				

Approved

Appendix B. Schedule of Assessments (continued)

(Part 3)

Study Procedures ^{a,r}	Week																											
	21	22	23	24	25	26	27	28	29	30	31	32	33	34	35	36	37	38	39	40	41	42	43	44	45	46	47	48
General Assessments^r																												
Vital Signs ^b	X		X		X		X		X		X		X		X		X		X		X		X		X		X	
PE, weight & ECOG ^b	X			X			X			X			X			X			X		X		X		X			
Review of AEs, SAEs, & conmeds ^d	X		X		X		X		X		X		X		X		X		X		X		X		X		X	
Local Laboratory Tests^{t,r}																												
Hematology	X		X		X		X		X		X		X		X		X		X		X		X		X		X	
Chemistry ^g	X ^g		X																									
PT and INR			X				X						X															X
HgbA1c	X			X			X			X			X			X		X		X							X	
TSH	X			X			X			X			X			X		X		X							X	
CEA				X									X								X							X
Central Laboratory Sample Collection^{h,r}																												
Antibodies ^{l,p}				X																								X
Investigational Product Administration^r																												
Review dose adjustment criteria ^m	X		X		X		X		X		X		X		X		X		X		X		X		X		X	
Investigational product administration ^m	X		X		X		X		X		X		X		X		X		X		X		X		X		X	
Radiological Assessments^{n,r}																												
CT/MRI - Chest, Abdomen, & Pelvis				X									X								X							X
Investigator Assessment of Tumor Response				X									X								X							X

Approved

Appendix B. Schedule of Assessments (continued)

(Part 3)

Study Procedures ^{a,r}	Week 49 until Radiographic Disease Progression Visits repeated every 12 weeks (unless otherwise indicated)												30-Day Safety Follow-up Visit (+3 day window)	60-Day Follow-up Visit (+14 day window)	LTFU (± 28 day window)	End of Study ^q
	1	2	3	4	5	6	7	8	9	10	11	12				
General Assessments^r																
Vital Signs ^b	X		X		X		X		X		X		X			
PE, weight & ECOG ^b	X			X				X					X			
Review of AEs, SAEs, & conmeds ^d	X		X		X		X		X		X		X			
Local Laboratory Tests^{t,r}																
Hematology	X		X		X		X		X		X		X			
PT and INR	X					X							X			
Chemistry ^g	X ^g		X		X ^g		X		X ^g		X		X ^g			
HgbA1c	X			X				X					X			
TSH	X			X			X						X			
CEA												X	X			
Central Laboratory Samples^{h,r}																
Biomarker													X	X		
Antibodies ^{l,p}													X	X	X ^l	X ^p
Investigational Product Administration^r																
Review dose adjustment criteria ^m	X		X		X		X		X		X					
Investigational product administration ^m	X		X		X		X		X		X					
Radiological Assessments^{n,r}																
CT/MRI - Chest, Abdomen, & Pelvis												X	X ^{np}			X ^{np}
Investigator Assessment of Tumor Response												X	X ^{np}			X ^{np}

Footnotes for [Appendices A & B](#) are on the following pages

Approved

Appendix A & B. Schedule of Assessments Footnotes

- a. **Study Procedures.** All treatment procedures must be performed within \pm 3 days of the planned visit.
- b. **Vital signs, PE, Height, Weight, ECOG.** Vital signs will include BP, resting pulse, respiration rate, and temp. Height will be collected at screening. See [Appendix E](#) for ECOG scale. For part 3, only ECOG is required at qualification.
- c. **ECG.** A 12-lead ECG will be performed at screening and should include HR, QRS, QT, QTc, and PR intervals.
- d. **AEs, SAEs, and Concomitant Medications.** AEs, SAEs, and con-meds should be reviewed at each study visit and recorded on the eCRF. All SAEs should be reported to Amgen within 24 hours. See [Section 9](#) for details.
- e. **Standard of Care.** Vitals, PE, ECOG, hematology, chemistry, CEA, pregnancy test, and CT or MRI scans of the chest, abdomen, and pelvis will be considered standard of care and may be performed before consent. However, for screening and baseline purposes, they must be performed within the timeframes specified ([Section 7.1](#)).
- f. **Local Laboratory Analytes.** See [Section 7, Table 6](#) for a complete list of laboratory analytes. The screening hematology and chemistry performed \leq 7 days before enrollment will be used as baseline. Urine or serum pregnancy test must be completed \leq 3 days before enrollment/randomization. Blood samples will be collected before each dose of investigational product, except for the post-infusion PK. The blood samples may be collected \leq 3 days before the dose of investigational product. However, for PK, it is preferred that the pre-infusion blood samples are collected on the day of investigational product administration.
- g. **Chemistry.** Glucose (non-fasting) is included as part of the chemistry assessment for all subjects. For subjects in part 2 and 3, a fasting glucose will replace the glucose assessment at screening, weeks 5, 9, every 4 weeks thereafter, and at the 30-day safety follow-up visit.
- h. **Central Laboratory Assessments.** Refer to the central laboratory manual(s) provided separately for instructions on the collection, processing, and shipment of tumor tissue, antibody, PK, and biomarker samples.
- i. **Tumor Tissue.** During screening, archived formalin-fixed paraffin-embedded colorectal tumor tissue (block or unstained slides) from the primary or metastatic site collected prior to the study will be submitted to the central laboratory along with the associated pathology report for evaluation of KRAS tumor status, if applicable, EGFr membrane staining and/or other exploratory biomarker analyses (see [Section 7.5](#)). See KRAS testing in [Section 7.1.1](#) for additional information on KRAS testing.
- j. **PK Assessments (Part 1).** Subjects enrolled in part 1 will undergo more intensive PK blood sample collection during weeks 5 through 6. This will require 4 extra visits. For all subjects enrolled in part 1, PK samples will be collected pre-panitumumab infusion^f and post-AMG 102 infusion (\pm 5 min. after end of infusion) at weeks 1, 5, 7, 13, 23, 47, and every 6 months thereafter during treatment. During week 5, PK samples will be collected at week 5, hours 24 (day 2), 48 (day 3), 96 (day 5), and 168 (day 8/week 6) post-end of AMG 102 infusion. A PK sample will also be collected at the 30-day and 60-day follow-up visit(s). Note: If a subject is receiving only one of the two investigational products on a day PK is collected, then a pre-and post-infusion blood sample will be collected.
- k. **PK Assessments (Part 2).** PK samples will be collected pre-panitumumab infusion^f and post-blinded investigational product infusion (\pm 5 min. after end of infusion) at weeks 1, 3, 5, 7, 13, 23, 47, and every 6 months thereafter during treatment. A PK sample will also be collected at the 30-day and 60-day follow-up visit(s). Note: If a subject is receiving only one of the two investigational products on a day PK is collected, then a pre-and post-infusion blood sample will be collected.

Approved

- I. **Antibody Samples.** Antibody samples will be collected at weeks 1, 7, 23, 47, and every 6 months thereafter during treatment, and at the 30-day and 60-day follow-up visits. See [Section 7.4](#) for additional antibody assessments in LTFU for subjects with a positive or neutralizing positive antibody result. Note: subjects treated on cohort 3 in part 2 that go onto receive treatment in part 3, will be tested for HAPA at the 30-day safety follow-up for part 3.
- m. **Investigational Product Administration.** Investigational product must be administered after all other study procedures (eg, laboratory sample collection), unless otherwise specified (eg, post-dose PK). After the first dose of investigational product, each subject will be assessed for dose adjustments (see [Section 6](#)). The Q2W schedule of all subsequent doses will be planned according to study day 1 or within \pm 3 days of the planned dose.
- n. **Radiological Assessments.** A CT or MRI of the chest, abdomen, pelvis, and all other sites of disease will be performed at weeks 8 (+1 week) and within \pm 1 week at weeks 12, 16, 24, 32, 40, and 48, and every 12 weeks thereafter until radiographic disease progression or the subject begins another treatment. Subjects with symptoms suggestive of disease progression will be evaluated for tumor response at the time symptoms occur. The same modality of imaging used at screening should be used throughout the study for direct comparison. Radiological images performed as standard of care \leq 35 days before enrollment may be used for screening purposes. All assessments will be made by the investigator using modified RECIST v1.0 (see [Appendix F](#)). Subjects with a complete response or partial response will have confirmatory radiological images performed no less than 4 weeks (28 days) after the criteria for response are first met. See footnote p below for LTFU imaging requirements.
- o. **Inclusion Criteria for Part 3.** Subjects initially randomized in part 2 that meet the criteria outlined in [Section 4.3](#) may be unblinded to determine their treatment assignment in part 2. Subjects assigned to Cohort 3 may be further randomized in part 3. The first dose of blinded investigational product must be administered \geq 2 weeks, but \leq 6 weeks (2 to 6 weeks) after the last dose of investigational product received in part 2. Any exceptions to the first dose of blinded investigational product should be discussed with and approved by Amgen prior to implementation. The first dose of part 3 investigational product must be received \leq 3 days after randomization in part 3. See [Sections 4.3](#) and [7.2](#), and [Appendix B](#).
- p. **LTFU.** After the 30-day safety follow-up visit, subjects will be followed for radiographic disease progression (if not documented previously) and survival every 3 months (\pm 28 day window) beginning after the 30-day safety follow-up and continuing for up to 2 years after the last subject is randomized in part 2 (see [Section 7.4](#) for details). See footnote I for additional information related to follow-up for positive antibodies to panitumumab, AMG 102, or AMG 479.
- q. **End of Study (subject).** The end of study for each subject is defined as the date the subject withdraws consent from study, completes the LTFU^P, or death. **The end of study for each subject who remains on study after the planned data snapshot of the final analysis is defined as date the subject withdrew consent from the study, completes the 30-day safety follow-up visit, or death.**
- r. **Study Procedures Following Completion of Data Snapshot of Final Analysis:** Data collection for subjects who remain on study treatment after the planned data snapshot of the final analysis has been completed will be limited to investigational product administration and serious adverse event reporting (see [Section 7.7](#) and [Section 9.3](#)). Other protocol-specified procedures and observations outlined in the Schedule of Assessments and in [Sections 7.1](#) through [7.6](#) of the protocol, including blood samples and radiographic imaging, will not be collected. However, the investigator, at his or her discretion, may continue to perform the procedures and observations outlined in [Section 7](#) and Schedule of Assessments per local institution standard of care.

Approved

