The subject treatment assignments in parts 2 and 3 will be unblinded after the planned data snapshot of the final analysis has been completed. Subjects receiving placebo will discontinue placebo administration and, in the absence of disease progression or unacceptable toxicities, may continue to receive investigational product (panitumumab AMG 102, or AMG 479, if applicable), Q2W at the investigator's discretion until disease progression, withdrawal of consent, death, or unless otherwise indicated by the study team. Data collection during this period will be limited to investigational product administration and serious adverse event reporting (see [Section 9.3](#)). Other protocol-specified procedures and observations outlined in the [Sections 7.1](#) through [7.6](#) and [Schedule of Assessments \(Appendices A and B\)](#), including blood samples and radiographic tumor imaging, will not be collected. However, the investigator, at his or her discretion, may continue to perform the procedures and observations outlined in the [Section 7](#) and [Schedule of Assessments](#) per local institution standard of care.

Primary and Secondary Endpoints:

Primary Endpoints:

Part 1: Subject incidence of DLTs

Part 2: Overall ORR

Secondary Endpoints:

Part 2:

- Duration of response
- Time to response
- Disease control

Approved

- Progression-free survival
- On-treatment progression-free-survival
- Overall survival
- Incidence of all AEs and clinical laboratory abnormalities
- Incidence of antibody formation to panitumumab, AMG 102, and AMG 479
- C_{\min} , C_{\max} , and AUC for panitumumab and AMG 102 (Part 1)
- C_{\min} and C_{\max} for panitumumab, AMG 102, and AMG 479 (Part 2)

Sample Size:

Part 1: Approximately 6 to 18 subjects (n = 6 to 9 per dose level of AMG 102 evaluated in combination with panitumumab).

Part 2: Approximately 126 subjects (n = 42 per cohort)

Part 3: Subjects from cohort 3 of part 2 will cross over to part 3 (n = 42)

Summary of Subject Eligibility Criteria:**Key Inclusion Criteria (Parts 1 and 2)**

- Man or woman \geq 18 years of age
- A life expectancy estimate of \geq 3 months
- ECOG 0 or 1
- Histologically or cytologically confirmed metastatic adenocarcinoma of the colon or rectum
- Wild-type KRAS tumor status of archival tumor tissue confirmed by an Amgen approved central laboratory or an experienced laboratory (local laboratory) per local regulatory guidelines using a validated test method

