- Major surgical procedure \leq 35 days before enrollment or minor surgical procedure \leq 14 days before enrollment. Subjects must have recovered from surgery related toxicities. Central venous catheter placement, fine needle aspiration, thoracocentesis, or paracentesis is not considered a major or minor surgical procedure.

See protocol [Section 4.3](#) for inclusion criteria for part 3.

Investigational Product Dosage and Administration:

Investigational product will be diluted in 0.9% sodium chloride. Investigational product will be administered by IV infusion beginning on week 1 and continuing Q2W until disease progression, intolerance, withdrawal, death, or unless otherwise indicated by the study team or DRT (see [Sections 6.7](#) and [6.8](#)). Note: Subjects in cohort 3 of part 2 may be eligible to receive treatment with blinded investigational product in part 3 (see [Sections 4.3](#) and [7.2](#)).

In parts 1 and 2, panitumumab will be administered IV by infusion pump through a peripheral line or indwelling catheter using a nonpyrogenic, low protein binding 0.2- or 0.22-micron pore size in-line filter (obtained by each center) infusion set up over 60 minutes \pm 15 minutes. The infusion time should be extended to 90 minutes \pm 15 minutes for doses higher than 1000 mg. Administration of panitumumab by methods other than infusion pump must be discussed and approved by Amgen prior to administration.

In parts 2 and 3, the blinded investigational product (AMG 102, AMG 479, and placebo) will be administered IV through a peripheral line or indwelling catheter using a nonpyrogenic, low protein binding filter with a 0.2- or 0.22-micron pore size in-line filter (obtained by each center) infusion set-up.

Following completion of the panitumumab infusion and proper flushing of the infusion line, AMG 102 (part 1) or blinded investigational product (part 2) will be administered IV over 60 minutes \pm 15 minutes.

If a dose of panitumumab and AMG 102 (part 1) or blinded investigational product (part 2) is well tolerated (ie, without any serious infusion-related reactions), then subsequent IV infusions may be administered over 30 minutes \pm 10 minutes.

These infusion times also apply to blinded investigational product (ie, AMG 102 or placebo, and AMG 479 or placebo) in part 3.

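### The post-infusion PK window is written as ±5 minutes around the end of infusion, which literally allows a draw while AMG 102 or AMG 479 is still running and can understate Cmax

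*Combined protocol and SAP*

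**What the plan says.** All references are to the current protocol version, the last in the combined document.

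- **Sampling window.** Footnote k to Appendices A and B (part 2) times the sample as "post-blinded investigational product infusion (\pm 5 min. after end of infusion". Footnote j (part 1) has "post-AMG 102 infusion (\pm 5 min. after end of infusion". The earlier protocol versions in the combined document carry the same ±5 minutes.
- **How the sample is described elsewhere.** Footnote f reads "Blood samples will be collected before each dose of investigational product, except for the post-infusion PK". Footnote m likewise treats it as a sample taken after dosing.
- **Endpoints.** The synopsis lists Cmin and Cmax "for panitumumab, AMG 102, and AMG 479 (Part 2") as secondary endpoints, and Cmin, Cmax "and AUC for panitumumab and AMG 102 (Part 1").
- **Infusion times.** The synopsis (Investigational Product Dosage and Administration) says "AMG 102 (part 1) or blinded investigational product (part 2) will be administered IV over 60 minutes \pm 15 minutes". If a dose is well tolerated, "then subsequent IV infusions may be administered over 30 minutes \pm 10 minutes".
- **Order of infusions.** The second product starts "Following completion of the panitumumab infusion and proper flushing of the infusion line".

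In part 2, footnote k schedules no further sample on the same day or in the days that follow, so this one draw supplies Cmax for the visit.

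**The concern.** A window centred on the end of infusion has a negative half. A sample taken there is drawn while the second product is still going in, before the concentration has peaked. The error runs one way only: an early draw can lower the observed Cmax of AMG 102 or AMG 479 but cannot raise it. With no later part 2 sample that day, nothing in the schedule would reveal or correct it.

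Five minutes is also not a fixed share of the dose. It is a small part of a 75-minute infusion and a large part of a 20-minute one. Shortened infusions are possible only after a tolerated dose, so the largest possible error differs between week 1 and later visits. Anyone comparing Cmax across visits or sites would be mixing exposure with sampling time and infusion length.

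**Working it through.** The plan gives no figure on this point, so there is nothing of its own to reproduce.

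**Inputs from the documents.** Earliest literal draw: 5 minutes before the end (footnotes j and k). Standard infusion: 60 ± 15, so 45 to 75 minutes. Optional shortened infusion: 30 ± 10, so 20 to 40 minutes. Dosing interval: 14 days.

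**Assumptions.** Constant infusion rate and one-compartment kinetics. Half-life is not in the documents and is taken as 3 to 20 days.

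**Step 1: share of the dose not yet delivered.** Formula: 5 / T, with T the infusion time in minutes.

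| T (min) | 5 / T |
|---|---|
| 75 | 6.7% |
| 60 | 8.3% |
| 45 | 11.1% |
| 40 | 12.5% |
| 30 | 16.7% |
| 20 | 25.0% |

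The first dose cannot be a shortened infusion, so week 1 is limited to 11.1%.

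**Step 2: from undelivered dose to Cmax.** From the second dose on, drug left from earlier doses is already present and is not missed by an early draw. Elimination over a few minutes is negligible, so

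shortfall in Cmax ≈ (5 / T) / (1 + R),

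where R is the residual from earlier doses relative to the rise produced by one dose. With q = 2^(−14 / half-life in days), R = q at the second dose and q / (1 − q) at steady state. For T = 20:

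| Assumed half-life | q | Second dose | Steady state |
|---|---|---|---|
| 3 days | 0.039 | 0.25 / 1.039 = 24.0% | 0.25 / 1.041 = 24.0% |
| 7 days | 0.250 | 0.25 / 1.250 = 20.0% | 0.25 / 1.333 = 18.7% |
| 14 days | 0.500 | 0.25 / 1.500 = 16.7% | 0.25 / 2.000 = 12.5% |
| 20 days | 0.616 | 0.25 / 1.616 = 15.5% | 0.25 / 2.601 = 9.6% |

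The worst case after the first dose is therefore about 10% to 24%. The steady-state range over the same half-lives is 6.4% to 16.0% for a 30-minute infusion and 3.2% to 8.0% for a 60-minute one.

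**Step 3: an average rather than the extreme.** If draws were spread evenly over ±5 minutes (an assumption), half would be early, by 2.5 minutes on average. The mean shortfall in the dose increment would be 0.5 × 2.5 / T: 6.3% at 20 minutes, 4.2% at 30 and 2.1% at 60.

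**Step 4: the positive side of the window.** A draw 5 minutes late loses 1 − 2^(−5 / half-life in minutes). That is 0.08% at 3 days (4,320 minutes) and 0.01% at 20 days (28,800 minutes). Only the negative side matters.

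**Step 5: panitumumab on two-product days.** Its infusion is complete before the second one begins, so no panitumumab dose is outstanding at the draw. The sample comes late for panitumumab, from about 15 minutes (20 − 5) to about 90 minutes (75 + 5, plus an assumed 10 for the flush) after its own infusion ends. With an assumed half-life of 3 to 14 days, the decline over that time is 0.05% to 1.4%.

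**The case against.** The strongest reply is that nobody would read the footnotes this way. Both describe a sample taken post-infusion and after its end, footnotes f and m agree, and the 168-hour part 1 sample in footnote j is also counted from the end of infusion. Only the symbol points the other way. Footnote h also sends sites to a central laboratory manual for collection instructions. That manual is not among the documents and may settle the timing. This stands in part: early draws are neither clearly intended nor shown to have occurred, so the defect is contradictory wording with a possible consequence. A clearer manual would still leave the protocol text in conflict with itself.

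The second reply is that 25% is a corner case, needing the shortest permitted infusion and the earliest literal draw. That stands. A reader might infer that Cmax could be off by a quarter. But shortening applies only after an earlier dose, and carry-over then reduces the shortfall.

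The third reply is that little depends on these values. That also stands. The 10 mg/kg AMG 102 dose was identified under an objective based on dose-limiting toxicities, accumulation is not a listed endpoint, and the response-rate rule does not use PK data. One window covers every part 2 cohort, placebo included, so no difference in timing between cohorts is shown.

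Finally, enrollment closed on 04 May 2009 (part 1) and 05 February 2010 (part 2), Appendix B schedules no PK sampling in part 3, and protocol blood sampling stops after the final-analysis snapshot (footnote r). Rewording now reaches few samples. That is right, and it makes the rule for data already collected the more useful half of the fix.

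**Conclusion.** A minor point, and it holds conditionally. The ±5-minute window contradicts the words around it and literally permits a draw before the infusion ends. If a site used that side of the window, the AMG 102 or AMG 479 Cmax from that visit is too low. At the earliest literal draw the shortfall is at most 11.1% at week 1. At later visits with a 20-minute infusion it is about 10% to 24%. Longer infusions and later draws give less. These figures assume a constant rate, one compartment and a half-life of 3 to 20 days.

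A reader might go further and say that Cmax is biased low in this trial, or that panitumumab Cmax is compromised too. The documents support neither. The first needs evidence of early draws. For the second, panitumumab is fully infused beforehand on two-product days and the delay costs about 1% or less over most of the assumed range (1.4% at most). On single-product days the footnotes restate no window, so nothing can be concluded.

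**What to change.** - **Wording.** In footnotes j and k, state the post-infusion window as 0 to +5 minutes after the end of the infusion, for any samples still to be taken. This leaves at most a 0.08% shortfall under the half-lives assumed above.
- **Data rule.** For samples already taken, compare the recorded draw time with the recorded infusion stop time. Leave out of the Cmax summary any AMG 102 or AMG 479 draw that precedes the stop, and report how many were left out. The documents supplied do not show whether both times were recorded. If they were not, say so beside the Cmax results.

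The cost is a few words in two footnotes and one rule in the PK analysis. A few early draws are lost from Cmax. No extra samples are needed, and no dose or infusion time changes.
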